**(2.) Project Title and Abstract**

A Randomized Controlled Trial Comparing Brief Peer Supported webSTAIR to Waitlist

This study will enroll 350 Veterans at a 2:1 ratio where 200 Veterans will be enrolled into a brief peer supported webSTAIR (BPS webSTAIR) and 100 will be supported into Waitlist. The purpose of the study is to assess the efficacy BPS webSTAIR in regard to four outcomes: reduction in PTSD and depression symptoms (measured by the PCL-5 and PHQ-8, respectively) and improvement in emotion regulation and work and social adjustment (measured by the DERS-16 and WSAS, respectively). The active treatment is a 6-session modular treatment that focuses on learning emotion management skills where Veterans will have 10 weeks to complete the treatment. Assessments will occur three times for those in webSTAIR: baseline, post-treatment (10 weeks after randomization) and 8-week follow-up. and twice for those on waitlist (baseline and 10 weeks after randomization). It is hypothesized that BPS WebSTAIR will be superior to WL on all four outcomes. Mixed Effects Models will be used to evaluate the outcomes.

**(3.) Purpose.**

The purpose of this randomized controlled trial is to assess the efficacy of a brief version of webSTAIR (BPS webSTAIR) supported by peers compared to a waitlist condition (WL). Brief peer supported (BPS) webSTAIR is a 6-modulen web-based transdiagnostic program that provides skills training in emotion regulation; participants in this condition will be able to contact a Veteran peer trained in the program to obtain general support plus guidance about program use and application of skills.

**(4.) Scientific Rationale**

An 11-module version of webSTAIR with therapist coaching (Ortigo & Cloitre, 2018) has provided pilot data that the program is effective in reducing symptoms of posttraumatic stress disorder (PTSD) and depression as well as improving emotion regulation and work and social adjustment. Pilot data indicate that initial gains are made in the first 6 sessions. In addition, qualitative interviews with Veterans who have completed the program indicate high satisfaction with these modules. This study will assess whether a shorter version of the treatment (6 rather than 11 modules) and with peer rather than professional coaching will be effective compared to a waitlist condition. The BPS webSTAIR program was developed with the aim of providing a treatment for trauma-related symptoms that is effective, brief, engaging and likely to be completed by the user. The reduction of the number of modules creates a briefer treatment than our current web-based program. In addition, data indicated that integrating Veteran peers into mental health programs leads to better engagement and greater retention (Koenig et al., 2016), providing the rationale for including Veteran peers rather than therapists (e.g., psychologists, social workers). Given the absence of findings that a brief, peer-supported version of webSTAIR provides improvement in the above symptoms, we followed recommendations for the development and testing of psychotherapies and used a waitlist control as an initial test of efficacy.

**(5.) Focus**

**(a) Specific research question(s).**

**Aim 1:** To establish the efficacy of BPS webSTAIR in improving symptoms of PTSD and depression, emotion regulation problems and work and social adjustment compared to a Waitlist Control.

Hypothesis 1a: Compared to WL, BPS webSTAIR will provide greater improvement in PTSD symptoms as measured by the PCL5 (primary outcome) and depression as measured by the PHQ-8 (secondary outcome). Assessments will be made at pre-treatment, post-treatment, and 8-week follow-up for webSTAIR participants and pre and post-treatment (or 10 weeks from randomization) for WL.

Hypothesis 1b: Compared to WL, BPS webSTAIR will provide greater improvement in emotion regulation as measured by the DERS-16 and overall functioning as measured by the work and social adjustment scale (WSAS) (secondary outcomes). Assessments will be made at pre-treatment, post-treatment and 8-week follow-up for webSTAIR participants and pre and post-treatment (or 10 weeks after randomization) for WL.

**(c) Product.**

It is proposed that the brief online therapy programs will be made available for free to Veterans through the Vets Prevail platform.

**(6.) Anticipated Impact.**

We anticipate that Veterans and other individuals with symptoms of PTSD and depression could potentially benefit in several ways by participating in this study. These benefits may include reduced symptoms of depression and PTSD and improved emotion regulation and work and social adjustment.

**(7.) Methods**

**(a) Study design and approach**

This is a two-condition randomized controlled trial comparing BPS webSTAIR to WL. Participants will be enrolled in a 2:1 ratio (BPS webSTAIR vs. WL). Participants will be recruited from among users of the Vets Prevail website. A special effort will be made to enroll women Veterans via relevant ads on Facebook and other social media. Vets Prevail is responsible for enrolling 300 Veterans (200 into webSTAIR, 100 into WL). As noted in the study contract, enrollment is defined as the number of participants who have been accepted into the study and randomized into a treatment condition. Vets Prevail is responsible for recruiting and screening veterans and alerting NCPTSD RA to make phone contact with Veteran at all relevant assessment periods (baseline, post-tx and follow-up). The NCPTSD RA will facilitate completion of verbal informed consent, describe program including goal of completing program in 10 weeks answer questions about the study and motivate engagement in the program. The NCPTSD RA will then read through the baseline questions and document the answers. At the end of the call, the RA will recommend to the Veteran that they enter the Welcome Module and provide guidance to them at that time if they are ready to begin program.

Individuals accepted into the study will either be provided with access to BPS webSTAIR or placed on waitlist. Participants in BPS webSTAIR will complete a posttreatment assessment and 2-month follow-up. Participants in the WL condition will

complete a second assessment at 10th week, conclude their involvement in the study and be offered the Vets Prevail coping program including the use of webSTAIR.

In the BPS webSTAIR condition, participants will first complete a welcome module to orient them to the program. After randomization, participants will have 10 weeks to complete the 6 modules. Every time the Veteran logs on they will have the opportunity to engage with a Veteran peer for support through the web program. Contacts can last for up to an hour. Veterans will receive a series of automated reminders and engagement emails that the Vets Prevail program sends at various points in the program.

(b) Population and sample, including control group, if applicable.

Participants will be 350 Veterans, where after attrition from baseline assessment we expect to enroll per condition (200 in BPS webSTAIR and 100 in Waitlist) across all gender identities who meet the following criteria:

Inclusion Criteria

1. Age 21 or older
2. Able to read/write English
3. Internet connection allowing stable access to VetsPrevail website
4. Have experienced at least one traumatic event as indicated in the PC-PTSD-5
5. A score greater than or equal to 3 on the PC-PTSD-5 **OR** greater than or equal to 2 on the PHQ2 on the screen.
6. Enrollment into the webSTAIR study must be completed within two weeks of completing screener/eligibility based on symptoms.

Exclusion Criteria

1. Currently receiving a trauma-focused intervention (PE, CPT, EMDR, WET) assessed during baseline
2. Being unlikely to benefit from therapy or Telemental health, for example:
  - Cognitive difficulties as indicated during baseline assessment.
  - Active psychosis as indicated during baseline assessment.

(c) Measures and Assessment Schedule

Measure	Items	Purpose	Time	Screen	Base Line	Sessions	Post-Tx	2M FU
Sociodems	19	Baseline Sample Characterization	5min	X				
LEC-5	16	Baseline Sample Characterization	5min	X				
PC-PTSD-5	5	PTSD Inclusion/Exclusion Criteria	2min	X				
PHQ-2	2	Depression Incl/Exclusion Criteria	1min	X				
PCL-5	20	Primary Outcome – PTSD	7min		X		X	X
PHQ-8	8	Secondary Outcome – Depression	5min		X		X	X
DERS-16	16	Secondary Outcome – Emotion Regulation	10min		X		X	X
WSAS	24	Secondary Outcome -work and social functioning	15min		X		X	X
DERS-6	6	Weekly Feedback	2min			X		

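### Does the baseline call send waitlist Veterans into the webSTAIR Welcome Module?

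*Combined protocol and SAP*

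**What the plan says.** In section (7.)(a) of the combined protocol and SAP, the research assistant (RA) obtains verbal consent, describes the program, and is to "answer questions about the study and motivate engagement in the program". Next, "The NCPTSD RA will then read through the baseline questions and document the answers". The call closes with the sentence at issue: "At the end of the call, the RA will recommend to the Veteran that they enter the Welcome Module". The rest of that sentence offers guidance on the spot to a Veteran who is ready to start. That condition concerns readiness, not arm.

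Allocation appears in the next paragraph, without a time: "Individuals accepted into the study will either be provided with access to BPS webSTAIR or placed on waitlist". The same section then says "In the BPS webSTAIR condition, participants will first complete a welcome module to orient them to the program". Waitlist Veterans complete their second assessment at week 10, after which they "conclude their involvement in the study and be offered the Vets Prevail coping program including the use of webSTAIR".

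On who enters the trial, the section states "Participants will be recruited from among users of the Vets Prevail website", and that "enrollment is defined as the number of participants who have been accepted into the study and randomized into a treatment condition". Section (7.)(b) assesses the exclusions during the baseline assessment. It expects 350 Veterans to yield 200 and 100 once losses from that assessment are taken off.

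**The concern.** Taken literally, the call has one script for everyone. It promotes the program and ends by pointing the Veteran to its first component, with no check on arm and no statement that randomisation has happened. Two opposite biases could follow in the waitlist arm.

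- **Exposure.** Participants are already users of the host website. If a waitlist account could open the module, controls would receive something from the active arm, which would tend to shrink the difference.
- **Disappointment.** If the account could not open it, a Veteran encouraged to begin and then told to wait might report worse symptoms at week 10, which would tend to widen the difference.

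Waitlist is the only comparator, Veterans know which arm they are in, and all four outcomes are their own questionnaire answers. The analysis plan in section (7.)(d) addresses neither route.

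**Working it through.** The plan gives no figure on this point to reproduce, so the check is to set the statements side by side.

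**1. When does randomisation occur?** Three statements place it after the baseline questions.
- Enrolment means accepted and randomised (section (7.)(a)).
- Exclusions are assessed during baseline (section (7.)(b)), so acceptance cannot sensibly come earlier.
- The arm sizes are counted after baseline losses: 350 − (200 + 100) = 50 Veterans, and 50/350 = 14.3%.

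None of these says whether randomisation comes before or after the closing recommendation.

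**2. If allocation is known by the end of the call.** The access sentence in section (7.)(a) splits accepted Veterans into those given webSTAIR and those placed on waitlist. A waitlist Veteran then has nothing to enter. To include that Veteran in the recommendation, one must read a single sentence apart from its neighbours.

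**3. If the recommendation comes before allocation.** Some Veterans would be pointed to the module and then made to wait. The text does not establish this order, and two details lean against it. Guidance into the module during the call presupposes that the Veteran can open it, and access is described as a result of allocation. The module is also described as a step within the webSTAIR condition, which has no members until someone is randomised.

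**4. Does an unqualified noun mean both arms?** Not reliably in this section. The same paragraph has the RA contact the Veteran at baseline, post-treatment and follow-up, yet waitlist participants have no follow-up assessment. The missing qualifier is therefore weak evidence that waitlist Veterans were meant.

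**5. How large could an effect be?** The only available number is the waitlist share, 100/(200 + 100) = 33.3%. It counts the people the wording could reach. It does not measure bias. The module's stated purpose is orientation, while the abstract describes the active treatment as six sessions of emotion management skills, so exposure to the module alone would be limited. Nothing in the documents quantifies disappointment, and the two routes act in opposite directions.

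**6. What would a reordered call gain?** One option is to move the motivational talk and the recommendation to after allocation, for webSTAIR Veterans only. A talk given before allocation is the same in both arms. Moving it would create a difference in staff contact between arms. Allocation would also have to be available and disclosed during the call, or a second contact arranged within the two-week enrolment window.

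**The case for a change.** The strongest case for a change is that a call script written directly from this paragraph would contain no arm check, and one clause would supply it. The access sentence implies that access follows allocation but describes no technical lock. The text mentions the welcome module before it starts the 10-week clock at randomisation, so a reader could place the module first. Even with access closed to controls, encouragement followed by waiting does not depend on what the module contains. With a single control arm and self-reported outcomes, a cheap safeguard seems reasonable.

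Part of this stands. The sentence is loose, the order is unstated, and a short clarification would do no harm. The claim that the recommendation reaches every Veteran whichever order applies does not stand. If allocation is known, the neighbouring sentences exclude waitlist Veterans. The disappointment route also has limited force. Waiting after consent is inherent in a waitlist control, which section (4.) justifies as an initial test of efficacy. What Veterans are told about the two arms belongs in the consent material, which is not in the reviewed text, so it cannot be assumed to be unbalanced.

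**Conclusion.** No change to the plan follows. The gap is one missing qualifier and one unstated time point. Staff would fill both from the same section by recommending the module to Veterans allocated to webSTAIR, once the baseline questions and exclusions are complete. The wording could at most touch the 100 waitlist Veterans of 300 (33.3%), but no exposure is shown and no bias can be sized or signed. Reordering the call is a debatable trade-off, because it replaces a talk common to both arms with one given to a single arm. This conclusion rests on two assumptions: that access to the module follows allocation, as section (7.)(a) indicates, and that randomisation follows the baseline assessment, as sections (7.)(a) and (7.)(b) together imply. If waitlist accounts could in fact open the module before week 10, the question of exposure would need to be looked at again.

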**Web Metrics (example constructs/data)**

Construct	Explanation
Module Completion	Per module; options of yes, no, partial
Time on Each Module	Time in minutes user spent in each module
Total Time in Entire Program	Time in minutes
NEW: Brief 6-item DERS Score at the beginning of each module	Sum of six items
Frequency of Accessing Each Skill	Frequency of each skill accessed/practiced outside of module
Time Spent on Each Skill	Time in minutes user spent in each skill
Frequency of requesting chat	Number of requests
Duration of average chat	Minutes
Total Time Spent in Chat	Minutes

**(d) Analysis Plan.**

**Overview:** The equivalence of the treatment conditions on baseline variables (demographics and psychological variables) will be assessed and controlled (if necessary) in the final analyses. Other preliminary analyses will include examination of distributional properties of the measures. We will use transformations to improve distributions when necessary. Missing data patterns (from missed assessments and from dropout) will be examined and compared between conditions. Mixed Effects Models (MEMs) will be used to evaluate differences between the two treatments over time with time as a main effect and treatment-by-time as an interaction term. Participants will be random.

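### Does the open-ended clause allowing outcomes to be transformed put the primary PCL-5 comparison at risk?

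*Combined protocol and SAP*

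**What the plan says.** The Analysis Plan, section (7.)(d), is one short paragraph. Among the preliminary steps it lists, "Other preliminary analyses will include examination of distributional properties of the measures", followed by "We will use transformations to improve distributions when necessary". It exempts no outcome, so the sentence covers the primary PCL-5 as well as the PHQ-8, DERS-16 and WSAS. It does not say what makes a transformation necessary, which one would be used, at which visit the distribution is judged, or whether arm is masked at that point.

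The next sentence is a separate matter: "Missing data patterns (from missed assessments and from dropout) will be examined and compared between conditions". It concerns missing data only.

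The outcomes are then analysed by mixed effects models "with time as a main effect and treatment-by-time as an interaction term". In section (5.), Hypothesis 1a predicts "greater improvement in PTSD symptoms as measured by the PCL5 (primary outcome"). It names the instrument but gives no difference in points and no other effect measure. No other section fixes the scale of analysis.

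**The concern.** An interaction depends on scale. Two participants who each improve by 10 PCL-5 points count equally in raw points, but on a root or log scale the one who started lower counts for more. Transforming the outcome therefore changes the quantity being estimated as well as the fit of the model. If the scale is settled after the trial data have been inspected, the primary result could appear on a scale nobody chose in advance, might not read in PCL-5 points, and might be significant on one scale and not on another. If the choice were swayed by the treatment result, type I error would also rise. With 200 and 100 participants per arm, moderate skew does not oblige anyone to transform, so fixing raw points in advance looks like an obvious and cheap improvement.

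**Working it through.** **Inputs.** From the documents: 200 randomised to webSTAIR and 100 to waitlist (Methods (a)), PCL-5 as primary outcome, treatment-by-time as the effect tested. The documents give no alpha, SD, effect size or PCL-5 distribution, so there is no stated figure to reproduce. Everything below that needs such a value rests on an assumption.

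**Step 1: does scale matter?** Compare a fall from 60 to 50 with a fall from 20 to 10.

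- Raw: 10 and 10, ratio 1.
- Square root: √60 − √50 = 0.675; √20 − √10 = 1.310; ratio 1.310/0.675 = 1.9.
- log(x+1): ln(61/51) = 0.179; ln(21/11) = 0.647; ratio 0.647/0.179 = 3.6.

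So the premise is right.

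**Step 2: is the test still valid?** With two visits and complete data, the interaction is the arm difference in change scores, tested by t = (d̄₁ − d̄₀)/√(s₁²/200 + s₀²/100) at an assumed two-sided 0.05. Assumed population: baseline gamma with shape 3 and scale 10 (mean 30, SD 17, skewness 0.9); post-treatment = 0.8 × baseline + normal error with SD 11; both rounded and bounded at 0 and 80. The rule studied takes whichever of raw, square root and log(x+1) is least skewed post-treatment. Under no effect (20,000 trials), type I error is 5.0% for raw points and 4.7% for the rule. With stronger baseline skew (1.3) the figures are 5.0% and 4.9%. A separate run of the first population gave 5.4% and 5.1%. Choosing by distribution does not inflate the error.

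Picking the scale with the smallest p-value would give 8.5%, or 7.6% to 8.8% in populations with mean 30 or 40 and SD 16. The plan does not describe that practice.

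**Step 3: does the rule lose power?** Same skewed population, average benefit 4 points, 5,000 trials per row:

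| Who benefits | Raw | Least-skewed rule | Trials where the two disagree on significance |
|---|---|---|---|
| Baseline 33 or more | 79% | 66% | 14.6% |
| In proportion to score | 82% | 76% | 10.1% |
| Everyone equally | 84% | 87% | 10.2% |
| Baseline below 33 | 85% | 97% | 12.0% |

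A separate run gave 77% against 64% for high scorers and 72% against 88% for low scorers. The level for low scorers shifts between runs, but the direction does not. Neither scale wins throughout, and the documents do not say who will benefit.

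**Step 4: is that the plan's rule?** No. Step 3 always takes the least-skewed scale, however small the gain. The plan transforms only if necessary. Suppose necessary means absolute skewness above 1 (an assumption). In this same skewed population, average post-treatment skewness is about 0.6 to 0.7. Judged post-treatment, the trigger fires in about 0.3% of trials or fewer, and raw and rule disagree on significance in 0.2% or fewer. Judged at baseline, it fires in about 12%.

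**Step 5: does the result need the assumed skew?** With a roughly symmetric baseline (assumed mean 38, SD 16), even the rule of step 3 keeps raw points in at least 99.8% of trials. Disagreement is 0.1% or less.

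**The case for a change.** The best case for acting is that a default without a criterion binds nobody. Two competent analysts could differ, and the visit at which skewness is judged matters: under the least-skewed rule, using baseline instead of post-treatment selects a different scale in 11% to 41% of trials with an effect, and in 50% with none. Entry requires a positive screen for PTSD or for depression, so some participants may enter on depression alone with low PCL-5 scores, which makes right skew plausible. A lax trigger in such a population would move towards the 10% to 15% disagreement of step 3. The remedy would be one sentence, and raw points read more easily.

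Part of this stands. The scale is not fully pre-specified, and a transformed analysis would estimate something other than a difference in points. But the percentages belong to a chosen rule and a chosen skew, neither of which is in the documents; requiring a positive screen also tends to remove low scorers, which works against right skew. Hypothesis 1a asks for greater improvement on the instrument, which can be tested on a monotone scale, although the estimand differs. The sentence about comparing conditions concerns missing data and is no evidence that transformations would be judged with arm revealed. If moderate skew at this sample size needs no transformation, as the concern itself says, the plan's own condition would seldom be met.

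**Conclusion.** No change is needed. The clause leaves a criterion unwritten, but its wording keeps raw scores as the default and makes distribution the only trigger, which analysts can apply sensibly. Followed as written, it is not shown to give a wrong or systematically worse result. Type I error stays near 5% (4.7% to 5.1% for the least-skewed rule). Disagreement with raw points is 0.2% of trials or fewer under a skewness threshold of 1 judged post-treatment, or under a roughly symmetric baseline. Fixing raw points is a trade-off: in the skewed population it gains 13 percentage points of power if high scorers benefit (79 − 66) and forgoes 12 if low scorers do (97 − 85).

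These figures rest on assumed distributions, effects, alpha and triggers, on two visits and on complete data. Only the PCL-5 was modelled, not the secondary outcomes. A laxer trigger combined with marked skew would bring more disagreement, but the documents give no reason to expect that combination.

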**(8.) Duration/Resources**

**Proposed Duration of Study:** The probable duration of the study will be approximately 24 months. We expect that it will take approximately 3 months to build and test the webSTAIR program, obtain IRB approval and hire and train staff, 17 months to recruit the participants and approximately 5 additional months to finish collecting the data (last cohort of participants which will take a maximum of 18 weeks to complete), and approximately 3 months to clean, analyze data and prepare reports.

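### Does leaving time coding and visit set open in the mixed model put the week-10 comparison with waitlist at risk?

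*Combined protocol and SAP*

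**What the plan says.** Section 7(d) is the whole analysis plan. It describes mixed effects models for "differences between the two treatments over time with time as a main effect and treatment-by-time as an interaction term", with participants as random. Time coding, the visits to be used and the primary contrast are not given, and no treatment main effect is listed.

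The Abstract sets assessments at "three times for those in webSTAIR: baseline, post-treatment (10 weeks after randomization) and 8-week follow-up. and twice for those on waitlist". Hypothesis 1a (section 5(a)) first states the comparison with waitlist on the PCL-5 (primary) and PHQ-8. A separate sentence then gives the schedule, ending "8-week follow-up for webSTAIR participants and pre and post-treatment (or 10 weeks from randomization) for WL". Hypothesis 1b does the same for the DERS-16 and WSAS. Under Study design and approach, waitlist participants have their second assessment at week 10 and then "conclude their involvement in the study and be offered the Vets Prevail coping program including the use of webSTAIR". Section 8 confirms the longest participation as 18 weeks, which is 10 + 8.

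**The concern.** Week 18 has no waitlist counterpart, yet it appears in the schedule sentence of each between-arm hypothesis, and the measures table marks it as a PCL-5 visit like the others. Someone reading section 7(d) alone could enter every visit and fit time as a straight line. The interaction would then compare a webSTAIR slope over 0 to 18 weeks with a waitlist slope over 0 to 10 weeks. If webSTAIR participants improve by week 10 and then hold steady, the flat stretch after treatment drags their slope down, and a real week-10 benefit could be missed. If improvement accelerated after week 10, the benefit would be overstated. Because the primary test rests on this one interaction, an open choice here deserves a check.

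**Working it through.** The plan gives no SD, effect size or power, so there is no stated figure to reproduce.

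**Inputs from the documents.** 200 webSTAIR and 100 waitlist; visits at weeks 0, 10, 18 and at weeks 0, 10.

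**Assumed.** Random intercept, correlation 0.5 to 0.7, complete data. For the illustration only: SD 15, mean PCL-5 change at week 10 of -8 (webSTAIR) and -3 (waitlist), so a true difference of -5, with webSTAIR staying at -8 at week 18.

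**Linear time in weeks, all visits, treatment main effect included.**

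- Mean webSTAIR visit time is (0 + 10 + 18)/3 = 9.33, so the deviations are -9.33, 0.67 and 8.67, with sum of squares 162.67.
- Weights for change per 10 weeks are 10 × deviation/162.67 = -0.574, 0.041, 0.533. Week 18 dominates and week 10 hardly counts. The waitlist week-10 mean has weight -1.
- Share of the webSTAIR week-10 change kept under a plateau: 0.041 + 0.533 = 0.574, so 43% is lost.
- Estimate: 0.574 × (-8) - (-3) = -1.59, against a true -5.
- Variance: SD² × (1 - ρ) × [100/(162.67 × 200) + 100/(50 × 100)], where 50 is the waitlist sum of squares. The SE is 1.61 at ρ = 0.5 and 1.25 at ρ = 0.7; power is 17% and 25%.

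**The same with only the listed terms (no treatment main effect).** Generalised least squares gives week-10 and week-18 weights of 0.170 and 0.461 (ρ = 0.5), or 0.118 and 0.490 (ρ = 0.7). The shares kept are 0.631 and 0.608, so 37% to 39% is lost. The estimates are -2.05 and -1.86, with power 31% and 37%.

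**The ordinary choices.** With visits as categories, or with only weeks 0 and 10 in either coding, the contrast is the difference in week-10 change.

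- Estimate: -8 - (-3) = -5, unbiased.
- SE with a treatment main effect: √[2 × SD² × (1 - ρ) × (1/200 + 1/100)] = 1.84 (ρ = 0.5) or 1.42 (ρ = 0.7); power 78% to 94%.
- If the baseline means are also constrained equal, the SE is 1.59 or 1.31 and power 88% to 97%. The plan does not state that constraint.

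**When the linear all-visit model is unbiased.** With time in weeks, it is unbiased if the week-18 change is 1.8 times the week-10 change: with -14.4 at week 18, 0.041 × (-8) + 0.533 × (-14.4) + 3 = -5.0. With visit numbers 0, 1, 2 the weights are -0.5, 0, 0.5, and the same course gives 0.5 × (-14.4) + 3 = -4.2 (about -4.3 without the main effect). The exception therefore depends on the time score used.

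**What must coincide for harm.** Three things: linear time, week 18 in the between-arm model, and webSTAIR change not linear in the chosen time score. The plan states none of them.

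**The case for a change.** The strongest case for a change is that no passage names week 10 as the comparison point, and that one permitted reading is seriously wrong. With no true difference (both arms -5 at week 10, webSTAIR holding it, SD 15), the linear all-visit model rejects in 26% to 40% of trials, nearly always in favour of waitlist. A primary test, the argument runs, should not rest on inference when a sentence or two would settle it.

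The arithmetic stands, and so does the omission. The inference, though, is short. The Abstract, the hypotheses and the design section each give waitlist only baseline and week 10, so a comparison with waitlist can be made nowhere else. The hypotheses assign the 8-week visit to webSTAIR participants in a sentence separate from the comparison. The measures table has no arm columns, so it implies no waitlist visit at two months. The sizes rest on an SD, correlation and trajectories from outside the documents, and the 26% to 40% needs both arms to improve and webSTAIR then to plateau; if neither arm changes, the rate is the nominal 5%. Insisting on categorical time would also be partly a matter of taste, since on the two shared visits both codings give the same result.

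**Conclusion.** No change follows. The plan is silent on time coding, visit set and contrast, and one reading of it would cost 37% to 43% of the webSTAIR week-10 change under a plateau (time in weeks, 200 and 100 analysed, complete data, random intercept, assumed correlation 0.5 to 0.7). That reading is not written anywhere. It joins a linear time score to a visit that only one arm attends, and no passage calls for it. An analyst who follows section 7(d) with the usual handling, and compares the arms where both are measured, gets a sound week-10 comparison, with week 18 left to describe maintenance within webSTAIR. Naming the week-10 contrast would make the text tidier, but it would only confirm the analysis that the design already points to. The conclusion would differ if the plan had specified linear time over all visits.
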